2.6.13. Linking of Treatment Emergent Adverse Events

All event records of the same preferred term from the same subject are to be linked by the onset date and the end date. If an event is followed by another event of the same preferred term with an onset date (or date/time) the same as or 1 day (or 1 minute if applicable) after the end date (or date/time) of the previous record and any features of the adverse event (i.e.: toxicity grades/seriousness/action taken) are different between these two records, these 2 records should be linked together and considered as 1 event.

2.7. General Analysis Specifications

Categorical variables are to be summarized using frequency counts and percentages. Continuous variables are to be summarized by the following descriptive statistics: mean, standard deviation, median and range (minimum and maximum).

3. INTERIM ANALYSIS AND DATA MONITORING COMMITTEE REVIEW

No formal interim analysis is planned. However, this interim data cut intends to support the BLA submission.

An independent data monitoring committee (IDMC) is used to make the RP2D dose recommendation based on the safety data in Phase 1. The IDMC and sponsor may decide to implement intermediate doses to ensure subject safety and better define the RP2D. The RP2D, as defined by the IDMC and sponsor, or the maximum dose tested will be the dose level at which subjects will be treated in Phase 2 of the study.

In both phases of the study, investigational product will be administered per schedule up to disease progression, intolerability, withdrawal, death, or unless otherwise indicated by IDMC.

4. SUBJECT INFORMATION

4.1. Demographics and Baseline Characteristics

Subject eligibility will be summarized for all subjects with a non-missing informed consent date. Number of subjects who did not meet all inclusion/exclusion criteria will be summarized, together with the specific non-met criterion. A listing of subjects who didn't meet all inclusion/exclusion criteria will be produced.

Patient enrollment will be summarized by country and site.

The following demographic and baseline characteristic panels will be summarized by dose group (2, 4, 8, or 16 mg/kg) and overall for Phase 1, and for the safety population for Phase 2:

- Demographics: age (continuous), age category (18 to < 65 years, 65 to < 75 years, and ≥ 75 years), sex (male, female), race (White, Black, Asian, Other, Not reported), ethnicity (Hispanic or Latino, Not Hispanic or Latino, Not reported), height (cm), weight (kg), baseline ECOG performance status (0, 1, 2).
- Baseline disease characteristics: type of myeloma (IgA, IgD, IgE, IgG, IgM, light chain, biclonal, other), ISS Staging (I, II, III), time since initial MM diagnosis (years), number of lytic bone lesions (None, 1-3, 4-10 more than 10), and bone marrow % plasma cells < 5, ≥5 − ≤ 10, >10 − ≤ 30, > 30).
- Disease related laboratory values: hemoglobin (g/L), hemoglobin category (< 80 g/L, 80 − 100 g/L, >100 g/L), platelets (giga/L), platelets category (< 75 giga/L, ≥ 75 giga/L), calcium (mmol/L), calcium category (>ULN, ≤ULN), corrected calcium (mmol/L), corrected calcium category ((>ULN, ≤ULN), creatinine (umol/L), creatinine category (> ULN, ≤ ULN), (mg/L), creatinine clearance (mL/min), creatinine clearance category (≥ 90, 60 < 90, 30 < 60, 15 < 30, < 15 mg/L), albumin (g/L), and albumin category (< 35 g/L, ≥ 35 g/L).

- Renal impairment using baseline creatinine clearance: Stage 1: ≥ 90 ml/min; Stage 2: 60 90 mL/min; Stage 3: 30 <60 mL/min; Stage 4: 15 <30 mL/min; Stage 5: < 15 mL/min

In addition, two panels of baseline laboratory tests will be summarized: hematology and serum chemistry.

The frequencies of CTC toxicity grade for these laboratory parameters at baseline will also be provided.

General medical history (including past and current conditions) will be summarized separately by body system and preferred term. Listing will be generated for abnormal medical history and prior surgeries.

Vital signs, including temperature, pulse, systolic and diastolic blood pressure at baseline will be summarized

ECG results at baseline will be summarized by overall interpretation: normal, abnormal and clinically significant, abnormal and not clinically significant.

4.2. Disposition Information

The number of patients, who were screened, enrolled and failed screening will be summarized overall. The reasons for screening failure will also be provided.

The number of patients who withdraw from study treatment (end of treatment information), including the reason for withdrawal from treatment, will also be summarized by dose group and overall for all treated subjects in Phase 1 and for the safety population in Phase 2.

All disposition and withdrawal data will also be listed.

4.3. Treatment Compliance

See Section 4.4.

4.4. Extent of Exposure

Descriptive statistics will be provided by dose group and overall for total number of pre-dose (Phase 1 only) and full daratumumab infusions, treatment duration (the interval between date of first infusion and date of last infusion), total dose (mg) received from pre-dose and full infusions, and relative dose intensity (calculated for each full-infusion as the ratio of dose intensity (mg/kg) and the planned dose level (mg/kg)).

The number and percent of patients with incomplete daratumumab infusions (i.e. total volume of infusion not administered) and reason for incomplete infusion will be summarized by dose group, visit and overall.

The duration of daratumumab infusions (hours) will also be summarized.

All infusions will be listed by patient and visit. For Phase 1, both pre-dose and full infusions will be listed.

Exposure to lenalidomide and dexamethasone (dose and duration) will be also summarized separately by dose group, visit and overall.

4.5. Protocol Deviations

Number of patients who did not meet all inclusion/exclusion criteria will be summarized, together with the specific non-met criterion. A listing of major protocol deviation will be provided.

4.6. Prior and Concomitant Medications

Only prior medications collected in this trial are the prior MM therapies as recorded on the CRF.

The number of lines of prior MM therapy will be summarized descriptively as well as by the following categories: 1, 2-3, >3. Frequency will also be presented for subjects with the following types of prior therapies: PI, IMiD, radiotherapy, steroids, lenalidomide, pomalidomide, thalidomide, bortezomib, carfilzomib, dexamethasone, prednisone, chemotherapy, alkylating agents, anthracyclines, and ASCT.

The incidence of refractory status to the most recent IMiD or PI will be provided (none, PI only, IMiD only, both PI and IMiD). The incidence of subjects that are refractory to the last line of therapy, alkylating agents, bortezomib, carfilzomib, lenalidomide, pomalidomide, and thalidomide will be provided separately.

In addition, a listing will be provided, including all prior multiple myeloma therapy.

Use of concomitant therapies and concomitant steroids therapy will be provided separately by therapeutic class, pharmacologic class, and preferred term. Additionally, a listing will be generated for all concomitant medications.

Pre-infusion medications will be grouped by analgesics, antihistamines, corticosteroids (long-acting, intermediate-acting), and other. Post-infusion medications will be grouped by analgesics, antihistamines, corticosteroids (long-acting, intermediate-acting). The incidence of pre-infusion and post-infusion medications will be presented by the aforementioned groups and preferred terms.

In addition, subsequent anticancer therapy will be summarized and listed similarly.

5. EFFICACY

5.1. Analysis Specifications

For Phase 1, all treated population will be used for all efficacy analyses.

For Phase 2, ITT/PP population will be used for efficacy analyses.

All categorical data will be presented as frequencies and percentages. The total number of patients in the population (N) will be used as the denominator for percentage calculations, unless stated otherwise in the table shell. Percentages will not be calculated for zero frequencies.

All continuous data will be summarized by using number of patients with available data to be summarized (n); mean; standard deviation (SD); median; minimum and maximum. In general, the minimum and maximum will be presented to the same number of decimal places as the raw data; the mean and median will be presented to 1 more decimal place than the raw data; the SD will be presented to 2 more decimal places than the raw data.

5.1.1. Level of Significance

No formal statistical test will be conducted.

5.1.2. Data Handling Rules

Efficacy assessment will be performed by sponsor per International Multiple Myeloma Working Group (IMWG) guidelines (Durie 2006, Rajkumar 2011). Response will be assessed by a computerized algorithm. An efficacy data listing will be generated to show the components for the response assessments.

Detailed data handling rules for efficacy assessment are provided in a separate computerized algorithm document: Disease Progression and Response Assessment.

5.2. Primary Efficacy Endpoint

Definition

Overall response rate (ORR) is defined as the proportion of patients with either complete response (CR, including stringent complete response [sCR]) or partial response (PR, including very good partial response [VGPR]).

The objective response according to the International uniform response criteria for MM as defined by Rajkumar et al ⁽¹⁾, will be determined the category of response (sCR; CR; VGPR; PR; SD) for each patient.

The definition of each response is given below.

Response subcategory		Response criteria
Stringent complete Response	Scr	 CR as defined below, plus Normal FLC ratio, and Absence of clonal PCs by immunohistochemistry or 2- to 4-color flow cytometry
Complete Response	CR ^a	Negative immunofixation of serum (or negative endogenous M-protein*) and urine, and Disappearance of any soft tissue plasmacytomas, and < 5% PCs in bone marrow *daratumumab interference test*
Very Good Partial Response	VGPR ^a	Serum and urine M-component detectable by immunofixation but not on electrophoresis, or ≥ 90% reduction in serum M-component plus urine M-component < 100 mg/24 hours
Partial Response	PR	 ≥ 50% reduction of serum M-protein and reduction in 24-hour urinary M-protein by ≥ 90% or to < 200 mg/24 hours If serum and urine M-protein are not measurable, a decrease ≥ 50% in the difference between involved and uninvolved FLC levels is require in place of the M-protein criteria If serum and urine M-protein are not measurable, and serum free light chain assay is also not measurable, ≥ 50% reduction in bone marrow PCs is required in place of M-protein, provided baseline percentage was ≥ 30% In addition to the above criteria, if present at baseline, ≥ 50% reduction in the size of soft tissue plasmacytomas is also required.
Minimal Response	MR ^b	 In patients with relapsed refractory myeloma adopted from the EBMT criteria: ≥ 25% but ≤ 49% reduction of serum M-protein and reduction in 24-hour urine M-protein by 50% to 89% In addition to the above criteria, if present at baseline, 25% to 49% reduction in the size of soft tissue plasmacytomas is also required No increase in size or number of lytic bone lesions (development of compression fracture does not exclude response)
Stable Disease	SD	Not meeting criteria for CR, VGPR, PR, or progressive disease

Key: CR = complete response; EBMT = European Group for Blood and Marrow Transplantation; FLC = free light chain; MR = minimal response; PC = plasma cell; PR = partial response; sCR = stringent complete response; VGPR = very good partial response.

Analysis Methods

ORR will be analyzed for all treated subjects in Phase 1, and for ITT and PP populations in Phase 2.

The number and percentage of patients in the following response categories will be tabulated by dose group and overall: sCR, CR, sCR + CR, VGPR, VGPR or better, PR, ORR, MR, ORR + MR, stable disease (SD), progressive disease (PD), and not evaluable (NE). For each of the above categories, two-sided 95% exact confidence interval (CI) will also be presented.

Subgroup analyses as specified in Section 2.4 will also be performed...

a) Clarifications to IMWG criteria for coding PD: Bone marrow criteria for PD are to be used only in patients without measurable disease by M protein and by FLC levels; "25% increase" refers to M protein, FLC, and bone marrow results, and does not refer to bone lesions, soft tissue Serumcytomas, or hypercalcemia and the "lowest response value" does not need to be a confirmed value.

Analysis Methods

TTP will only be analyzed for Phase 2.

Median time to progression will be estimated using the Kaplan-Meier method for the ITT population. No inferential analysis will be performed.

The Kaplan-Meier estimates will be plotted to produce a survival curve.

As an exploratory analysis, same TTP analyses are repeated based on investigator assessment, where PD was determined by study investigators.

5.3.2. Duration of Response

Definition

Duration of response is calculated from the date of initial documentation of a response (PR or better) to the date of first documented evidence of progressive disease, as defined in the IMWG

criteria. Relapse from CR is not considered as disease progression. Deaths due to disease progression will be treated as an event on the date of death, unless disease progression is documented before death. Patients who start subsequent therapy for MM will be censored at the last disease assessment prior to the start of subsequent therapies (inclusive). Patients, who are lost to follow-up, withdraw consent, withdraw from study without disease progression, or die due to causes other than disease progression will be censored at the last disease assessment date.

Analysis Methods

Duration of response will only be analyzed for Phase 2.

Duration of response will be estimated using the Kaplan-Meier method for the responders in ITT population. The same analysis will be repeated for the PP population as the sensitivity analysis.

No inferential statistics will be provided. A swim lane plot for responders will also be produced.

5.3.3. Progression-Free Survival

Definition

Progression free survival (PFS) is defined as the time between the date of first dose of daratumumab and either disease progression or death, whichever occurs first. Relapse from CR is not considered as disease progression. Subjects who start subsequent therapies for multiple myeloma will be censored at the last disease assessment that is not later than the start of subsequent therapies. Subjects who withdraw from the study before disease progression will be censored at the last disease assessment. Subjects who complete the study, have not progressed, and are still alive at the cut-off date of the analysis will be censored at the last disease assessment. All subjects who were lost to follow-up before the end of the study will be censored at the time of the last disease assessment. Patients with no post baseline disease assessment will be censored on Day 1.

Analysis Methods

PFS will only be analyzed for Phase 2.

PFS will be estimated using the Kaplan-Meier method for the ITT population. No inferential analysis will be performed.

The Kaplan-Meier estimates will be plotted to produce a survival curve.

As an exploratory analysis, same PFS analyses are repeated based on investigator assessment, where PD was determined by study investigators.

Kaplan-Meier estimates will also be plotted to produce the survival curves for responder vs. non-responder based on computerized algorithm.

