Visit Window	_		_	±1d	±1d	±1d	±4d	±1d	±1d	±1d	±4d	±1d	±4d	±7d	±2d	±7d
Response Assessments			X	X	X	X	X									
Bone marrow aspirate/bone marrow biopsy ^f	X^{g}										X ^g				X ^g	
IgA, IgM, IgG (M- component serum)	X°		Xº		Xº		Xº				Xº		X	Xº	Xº	
M-component (24-hour urine sample) ^m	X		X				X				X		X	X	X	
Free light chain kappa, lambda, and ratio (serum)	X		X		X		X				X		X	X	X	
New cancer assessment ⁿ																X
New antimyeloma treatment ⁿ																X
Survival ⁿ																X

Key: ADCC = antibody-dependent cell-mediated cytotoxicity; CDC = complement-dependent cytotoxicity; CT = computed tomography; d = day; ECG = electrocardiogram; ECOG = Eastern Cooperative Oncology Group; EOT = End of Trial; FU = Follow-up; Ig = immunoglobulin; w = week

- ^a All cycles are 28-day cycles: the first visit of a cycle should be 4 weeks after the start of the previous cycle.
- Informed consent may be obtained outside of the Screening Visit window, ie, before the Screening Visit date.
- Signs and symptoms (nonserious adverse events) occurring between the Screening Visit (before the first infusion) and the first study drug treatment at Cycle 1 Visit 1 should be recorded as medical history.
- d Vital signs are to be measured on days when daratumumab infusions are administered; before the start of the daratumumab infusion and at the end of the infusion.
- ^e Electrocardiograms (ECGs) will be performed at the Screening Visit (before the first infusion), before and after daratumumab infusion on Day 1 of each cycle, and at the EOT Visit. Three baseline ECGs should be performed before the first infusion of study drug. Before the ECGs are recorded, the subjects must be resting in a horizontal position for at least 20 minutes
- The computed tomography scan and bone marrow biopsy/aspirate may have been performed within 6 weeks before Cycle 1 Visit 1.
- To be completed at Screening for clinical staging, at Cycle 3 Day 1, and to confirm sCR, CR, or relapse from CR. May also be performed to investigate new symptoms or at the physician discretion. A portion of the bone marrow aspirate or biopsy will be utilized for biomarker analyses.
- b Unless otherwise stated, all blood and urine samples must be taken before administration of daratumumab. Samples must be sent to the central laboratory.

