4.2. Inclusion Criteria

Before entering Phase 1 of the study, subjects must:

- 1. Have relapsed multiple myeloma after receiving a minimum of 2 and a maximum of 4 prior lines of therapy and be eligible for treatment with Len/Dex.
- 2. Have measurable levels of M-component, defined as serum M-component $\geq 1.0 \text{ g/dL}$ and/or urine M-component $\geq 200 \text{ mg/24-hour sample}$.
- 3. Be \geq 18 years of age.
- 4. Have an Eastern Cooperative Oncology Group (ECOG) performance status of 0, 1, or 2 (Attachment 1).
- 5. Have a life expectancy of ≥ 3 months.
- 6. Provide signed informed consent after receipt of oral and written information about the study and before any study-related activity is performed.

Before entering Phase 2 of the study, subjects must:

- 1. Have received at least 1 prior line of therapy for multiple myeloma (refer to Attachment 2).
 - Have achieved a response (PR or better) to at least one prior regimen.
 - Have documented evidence of progressive disease (PD) as defined by the IMWG criteria on or after their last regimen.
- 2. Have measurable levels of M-component, defined as serum M-component $\geq 1.0 \text{ g/dL}$ and/or urine M-component $\geq 200 \text{ mg/24-hour sample}$.
- 3. Be \geq 18 years of age.
- 4. Have an ECOG performance status score of 0, 1, or 2 (Attachment 1).
- 5. Have a life expectancy of ≥ 3 months.
- 6. Provide signed informed consent after receipt of oral and written information about the study and before any study-related activity is performed.

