11.4. Efficacy Analyses

Response to treatment will be determined by the sponsor in accordance with the guidelines provided in Attachment 5. The proportion of subjects with response to treatment (stringent CR [sCR], CR, very good PR [VGPR], and PR) will be estimated. The quality of response (also including subjects who achieve MR) will be summarized. Subjects for whom response cannot be evaluated will be categorized as not evaluable. A determination of not evaluable will count as nonresponse to treatment. The proportions will be presented with corresponding exact 2-sided 95% confidence intervals.

Duration of response, time to progression, and PFS will be estimated using Kaplan-Meier techniques. Data for these variables will be censored in accordance with the FDA guidance on clinical study endpoints for the approval of cancer drugs and biologics (FDA 2011).

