5.3.5. Overall Survival

Definition

Overall Survival (OS) is defined as the number of days from administration of the first dose (Day 1) to date of death.

Data for patients who are alive at the date of last contact or have unknown status will be censored at the date of the last contact. Those patients who have withdrawn will be considered to be alive and censored at the date of withdrawal.

Analysis Methods

OS will only be analyzed for Phase 2.

OS will be estimated using the Kaplan-Meier method for the ITT population. No inferential analysis will be performed.

The Kaplan-Meier estimates will be plotted to produce a survival curve.

Kaplan-Meier estimates will also be plotted to produce the survival curves for responder vs. non-responder based on computerized algorithm.

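### SAP 5.3.3 gives two conflicting instructions for a subject who dies before any post-baseline disease assessment: count a PFS event, or censor on Day 1

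*SAP*

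**What the plan says.** The relevant text is in the definition paragraph of SAP 5.3.3.

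- **Event.** PFS ends at "either disease progression or death, whichever occurs first". Nothing there requires an assessment before the death.
- **Day 1 rule.** The last sentence reads "Patients with no post baseline disease assessment will be censored on Day 1". It is not limited to subjects who are alive.
- **A neighbouring rule that is limited.** For study completers, the rule covers only those who "have not progressed, and are still alive at the cut-off date of the analysis will be censored at the last disease assessment".
- **Analysis.** Phase 2 only: "PFS will be estimated using the Kaplan-Meier method for the ITT population. No inferential analysis will be performed".

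Elsewhere, Protocol 11.4 leaves the censoring of PFS to an outside source: "Data for these variables will be censored in accordance with the FDA guidance on clinical study endpoints". SAP 5.1.2 places the detailed handling rules for efficacy assessment in a separate algorithm document. Neither text is part of the protocol or SAP.

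**The concern.** A subject who dies before the first post-baseline assessment satisfies both the event definition and the Day 1 rule, and the SAP states no order of precedence. The restriction to living subjects in the neighbouring rule makes its absence from the Day 1 rule easier to read as deliberate. A programmer who applies the last sentence as written would take the subject out of the risk set at the start and lose the event.

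The resulting error runs in one direction only: it raises the PFS estimate. SAP Section 3 says the data cut is meant to support a licence application, so the rule should not be left to the programmer's choice.

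**Working it through.** **1. The plan's own figures.** There is no design calculation for PFS. The only one is for overall response rate (SAP 1.4): about 30 subjects, 50% against 75% or 80%, two-sided alpha 0.10. With an exact one-sample binomial and success at 20 or more of 30:

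- P(X ≥ 20 | 0.50) = 0.0494
- P(X ≥ 20 | 0.75) = 0.894 (stated 89%)
- P(X ≥ 20 | 0.80) = 0.974 (stated 97%)

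The stated power reproduces, and it does not depend on the PFS rule.

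**2. The rules side by side.** Take a Phase 2 subject who dies of progression before any post-baseline assessment.

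| Source | Outcome |
|---|---|
| Time to progression, SAP 5.3.1 | Event on the date of death; no Day 1 rule |
| Overall survival, SAP 5.3.5 | Event; no Day 1 rule |
| PFS definition, SAP 5.3.3 | Event |
| PFS last sentence, SAP 5.3.3, read literally | Censored on Day 1 |

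Read literally, the subject is an event for time to progression and for survival but not for PFS. That is incoherent, because PFS should contain every time-to-progression event. The same Day 1 sentence in SAP 5.3.4 (time to response) causes no conflict, because death is not an event there.

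**3. Size.** Inputs: N = 30 (SAP 1.4); k = deaths before any assessment (assumed); S = PFS among the other 30 − k subjects at the time of interest (assumed).

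- Deaths counted as events: PFS = (30 − k)/30 × S
- Deaths censored on Day 1: PFS = S, with 30 − k at risk
- Difference: k × S/30

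| k | S = 60% | S = 75% | S = 90% |
|---|---|---|---|
| 0 | 0 | 0 | 0 |
| 1 | 58.0 vs 60: 2.0 points | 72.5 vs 75: 2.5 points | 87.0 vs 90: 3.0 points |
| 2 | 56.0 vs 60: 4.0 points | 70.0 vs 75: 5.0 points | 84.0 vs 90: 6.0 points |

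For the median, assume the others follow an exponential with an 18-month median, and let f = (30 − k)/30. Counting the deaths gives 18 × ln(0.5/f)/ln(0.5) = 17.1 months for k = 1 and 16.2 for k = 2. Day 1 censoring gives 18.

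**4. How often it could arise.** In the Phase 2 schedule (Protocol Table 2), serum M-component and free light chains are next measured after Cycle 1 Day 1 at week 2, within a day either way. An earlier response mark is shown at week 1. If the schedule is kept and these samples count as disease assessments, the window is about 14 days. With exponential survival of median m months (assumed), p = 1 − 0.5^(14/(30.4375 m)):

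| m | p | Expected deaths, 30p | P(at least one) |
|---|---|---|---|
| 12 | 0.0262 | 0.79 | 55% |
| 24 | 0.0132 | 0.40 | 33% |
| 36 | 0.0088 | 0.27 | 23% |

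A constant hazard from Day 1 may overstate early risk, since Protocol 4.2 requires ECOG status 0 to 2 and a life expectancy of at least 3 months.

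**The case against.** The strongest reply is that the literal reading proves too much. In the same paragraph, the rule for subjects who start subsequent therapy does not say that they must be free of progression, and neither does the rule for loss to follow-up. Taken literally, the first would censor subjects who progressed and then changed treatment, which would defeat the endpoint. The paragraph works only if censoring applies where no event has already occurred, and on that convention the early death is kept. The outside guidance or the separate algorithm document may also settle the case.

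Much of this stands. A reader might infer that the plan definitely deletes early deaths; the documents do not support that, because the definition in the same paragraph says the opposite. What remains is that the convention is nowhere stated and that one neighbouring rule does carry the restriction to living subjects. The unseen documents cannot be relied on either way.

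A reader might also infer that toxic deaths would be hidden. The documents give no data on the cause of early deaths. Deaths are reported in several other places: SAP 6.2 covers all deaths by cause, deaths within 30 days of the last study drug, and a listing; SAP 6.1.1 covers deaths due to adverse events. Overall survival counts them too: "Overall Survival (OS) is defined as the number of days from administration of the first dose (Day 1) to date of death". The primary endpoint is adverse event incidence (Protocol 9.3).

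**Conclusion.** SAP 5.3.3 contradicts itself for a subject who dies before any post-baseline assessment, and the text available does not resolve it. It is a drafting defect of low severity. Under the literal reading each such death among 30 subjects raises the PFS estimate by S/30, and with no such death nothing changes. The number of early deaths and the level of PFS are assumptions, so the figures in the working show what could happen and do not estimate a bias in this trial. The effect is confined to a window of about 2 weeks and to a secondary endpoint with no test attached; no decision rule in the plan depends on it.

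**What to change.** Amend SAP 5.3.3 in two places.

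1. Restrict the Day 1 rule to subjects with no disease assessment after baseline who have not died.
2. State that a death without prior progression or subsequent myeloma therapy is a PFS event on the date of death, including when no assessment was made after baseline.

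The exception for subsequent therapy is needed. Without it, a subject who was never assessed, changed treatment and died later would become an event, against the subsequent-therapy rule in the same paragraph. The SAP should also say where that subject is censored. Day 1 is the natural place, because there is no later assessment to use.

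The separate algorithm document should be checked for agreement. The cost is a clause and a sentence in the SAP. No new data are needed, and the power statement is unaffected.
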